### 8.2.1 Primary Endpoints

- **Acute Safety**

The primary safety endpoint is the incidence of PAEs (within seven (7) days of the initial mapping and ablation procedure). PAEs include the following AEs:

Atrio-Esophageal Fistula*	Phrenic Nerve Paralysis (permanent)
Cardiac Tamponade/perforation	Pulmonary Vein Stenosis*
Device or procedure related death*	Stroke/CVA
Major Vascular Access Complication/Bleeding	Thromboembolism
Myocardial Infarction	Transient Ischemic Attack (TIA)
Pericarditis	

\* Device or procedure related death, pulmonary vein stenosis and atrio-esophageal fistula that occur greater than one week (7 days) post-procedure are considered and analyzed as PAEs.

A 14% performance goal is set for the primary safety endpoint

- **Long term effectiveness:**

Freedom from documented (symptomatic and asymptomatic) atrial arrhythmia (AF, AT or AFL) episodes based on electrocardiographic data ( $\geq 30$  seconds on arrhythmia monitoring device) during the effectiveness evaluation period (Day 91-Day 365). Acute procedural failure (i.e., failure to confirm entrance block, with or without touch-up, in all PVs except those that are silent and/or cannot be cannulated post-procedure) will be considered a long-term effectiveness failure.

A 50% performance goal is set for the primary long-term effectiveness endpoint

Further refer to appendix 1 for definitions on long term effectiveness terms.

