#### **For Primary Safety Endpoint:**

The primary safety endpoint analysis performed at this interim will include 3-month safety follow-up for all mITT-Wave II subjects and will be the same as the final safety endpoint analysis.

A beta-binomial model with a non-informative uniform prior will be used for the primary safety rate. The uniform prior for the safety rate will be updated based on the observed number of events to obtain the posterior distribution for the primary safety rate. If the posterior probability of the safety rate being less than 14% is greater than 0.975, the early success primary safety endpoint will have been met.

The null and alternative hypotheses for the safety endpoint for the early success interim analysis are:

$$H_0: \Pr(P_s < 0.14) \leq 0.975$$

$$H_a: \Pr(P_s < 0.14) > 0.975$$

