#### **For Primary Safety Endpoint:**

The final primary safety endpoint analysis is the same analysis performed at the early success interim as all safety data is available at the time of the early success interim look. A beta-binomial model will be used for this analysis. A non-informative uniform prior will be assumed for the primary safety proportion. The primary safety endpoint will be considered a success if

$$\Pr(P_S < 0.14) > 0.975$$

The analysis population for the primary safety endpoint will be the mITT-Wave II analysis set. If the posterior probability of the safety rate being less than 14% is greater than 0.975, then the study will be considered to have demonstrated safety of the device.

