7.4.1.2 Final Analysis of Primary Safety Endpoint

If early success is not achieved, then the final primary safety endpoint analysis will be performed at the end of the study.

The final analysis for the primary safety endpoint will use a beta-binomial model with a non-informative uniform prior Beta (1,1). At the time of the final analysis, the primary safety endpoint will be considered as success if:

$$\Pr(p_S < 0.14|y, n) > 0.975$$

where p_s is the PAE rate. If the posterior probability of the safety rate being less than 14% is greater than 0.975 then the study will be considered to have demonstrated safety of the device.

To investigate the robustness of the analysis result, the following sensitivity analyses will be performed in the FAS and mITT analysis sets unless otherwise noted at the time of the final safety analysis:

- **Sensitivity to Analysis Set**

The primary safety endpoint will be analyzed in the FAS as a sensitivity analysis.

- **Snap-Shot Binomial Analysis**

The number and percentage of subjects with primary safety events will be presented along with one-sided 97.5% exact binomial upper confidence bounds. Subjects with missing outcomes will be excluded from the analysis. Missing outcomes of primary safety endpoints is defined in Section 7.4.3.

- **Best-case Scenario**

The point estimate for the PAE rate will be estimated by treating subjects with missing primary safety outcomes as free from primary safety events.

- **Worst-case Scenario**

The point estimate for the PAE rate will be estimated by treating subjects with missing primary safety outcomes as failures.

- **Tipping Point Analysis**

Tipping point analysis will be performed for the primary safety endpoint to assess the impact of missing outcomes on the safety conclusion. The posterior distribution will be updated each time treating a subject with a missing outcome as failure to evaluate whether a tipping point is identified.

If early success is achieved, the primary safety endpoint and associated sensitivity analyses based on full 12-month follow-up data will be summarized descriptively.

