7.4.3 Handling of Missing Data

Missing data will be queried for reasons and handled on an individual basis.

- **Sample Size Selection Interim Analysis:** For the sample size selection interim analyses, subjects with incomplete follow-up data for the effectiveness endpoint will be censored at the time of their last follow-up visit, and only their observed partial follow-up time will contribute to the estimation of model parameters and compute the predictive probability of the effectiveness success.
- **Early Success Primary Safety Endpoint:** For the early success interim analysis of the safety endpoints, if a subject's 3-month follow-up is not complete but a PAE has occurred prior to 3-month follow-up, the subject will be considered as having an event. If a subject exits the study without completing their 3-month follow-up visit and the subject has not had a PAE, that subject will be excluded from the early success safety analysis.
- **Early Success Primary Effectiveness Endpoint:** For the early success interim analysis of the effectiveness endpoints, subjects with incomplete follow-up data will be censored at the time of their last follow-up visit (if event-free). For these subjects, only their observed partial follow-up time will contribute to the estimation of model parameters. Subjects who refuse the remote arrhythmia/holter monitoring device will be excluded from the early success effectiveness analysis.

- **Final Primary Safety Endpoint:** For the final primary safety analysis, if a subject does not have full 12 months of follow-up and the subject has had a PAE at any time during the follow-up, the subject will be considered an event. If a subject does not have 12 months of follow-up but has at least 3 months of follow-up (similar to early success interim), this subject's last observed status will be carried forward for the 12-month safety endpoint as a proxy. If a subject without a PAE does not have at least 3 months of follow-up, this subject will be considered as missing the primary safety endpoint and will be excluded from the final primary safety analysis.

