10.4 Interim Analyses for Early Success

One interim analysis is planned for an early success claim. The interim analysis will be performed when the first 30 subjects complete full follow-up of one year and all subjects in the MITT analysis set complete 3 months of follow-up. For the safety endpoint, the outcome for all patients will be known at the time of this interim analysis and the test will be final primary safety analysis.

At the interim analysis, the trial will declare early success if:

1. The safety objective is met.
2. Posterior probability of the effectiveness proportion p_E being greater than 50% is greater than 0.9975.

The posterior probability is estimated based on the proposed model in the next section.

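### The plan does not settle which safety test is confirmatory: late primary adverse events enter the 14% test, or do not, depending on the passage followed and on the effectiveness result

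*SAP*

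**What the plan says.** **Early-look test is final.** SAP (Wave II) 10.4 states that the safety outcome of all patients will be "known at the time of this interim analysis and the test will be final primary safety analysis". Protocol 20.4.4.2 says the early analysis "will include 3-month safety follow-up for all mITT-Wave II subjects and will be the same as the final safety endpoint analysis". Protocol 20.4.4.3 says: "The final primary safety endpoint analysis is the same analysis performed at the early success interim as all safety data is available".

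**Later test, on one path only.** SAP 7.4.1.2: "If early success is not achieved, then the final primary safety endpoint analysis will be performed at the end of the study". It uses the same rule, Pr(p_S<0.14)>0.975. SAP 7.4.3 makes this a 12-month analysis: for a subject without full follow-up, if "the subject has had a PAE at any time during the follow-up, the subject will be considered an event", and an event-free subject with at least 3 months is kept with the last status carried forward. On the other path: "If early success is achieved, the primary safety endpoint and associated sensitivity analyses based on full 12-month follow-up data will be summarized descriptively".

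**What counts.** Protocol 8.2.1 stars three components (death related to device or procedure, PV stenosis, atrio-esophageal fistula) "that occur greater than one week (7 days) post-procedure are considered and analyzed as PAEs". No end date is given. SAP 7.4.1.1 repeats that all safety outcomes are known at the look, then names these same three as exceptions and expects the interim and final tests to differ hardly at all. Protocol Table 6 calls phrenic nerve paralysis permanent only once documented at 12 months or later.

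**Missing data.** Protocol 20.4.4.4 excludes event-free subjects with less than 12 months from the primary safety analysis. That does not fit a test completed on 3-month data, nor the SAP's carry-forward.

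**The concern.** Safety is half of the success rule, and early success triggers CE-mark filing (protocol summary, Statistical Analysis). The look requires 12 months of follow-up in only 30 subjects and 3 months in the rest, so some events that belong to the endpoint cannot yet be known.

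Under the SAP, the confirmatory safety endpoint therefore has partial follow-up when effectiveness crosses 0.9975 and 12-month follow-up when it does not. If safety passes at the look and effectiveness misses 0.9975, SAP 10.4 and protocol 20.4.4.3 say safety is already decided, while SAP 7.4.1.2 says it is tested again. The same trial can then have two opposite safety verdicts, each supported by the plan.

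**Working it through.** **1. Reproduce the plan's figure.** Inputs: Beta(1,1) prior and threshold 0.975 (SAP 7.4.1.1), true rate 7%, goal 14% and 5% yearly dropout (SAP 10.2), and the sample-size mix in Table 3.a at 65% effectiveness (0.5535, 0.2854, 0.1611 for N=180, 255, 330). For each evaluable n, find the largest y with P(Beta(1+y, 1+n−y)<0.14)>0.975, then take P(Bin(n, 0.07)≤y), averaged over binomial retention and the mix. Result: 0.883 with 12 months of dropout and 0.886 with 3 months. Table 3.a gives 0.8853, so the rule is read correctly.

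**2. Follow-up at the look** (realistic schedule, SAP Appendix Table 1; dropout and roll-ins left aside).
- The 30th subject enters at month 2 + 12/13.5 = 2.9, so reaches 12 months at 14.9.
- N=180 is reached at month 9 + 24/30 = 9.8. The look is at 14.9, and 150/180 = 83% have less than 12 months.
- N=255 is reached at month 12 + 9/30 = 12.3. The look is at 15.3; about 33 subjects had entered by month 3.3, so 222/255 = 87% are short.
- N=330 is reached at month 15. The look is at 18; 72 had entered by month 6, so 258/330 = 78% are short.

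**3. Acceptance limit.** With 5% yearly dropout to 3 months, n = N × 0.95^0.25:

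| N | n | most PAEs that pass | posterior | with one more PAE |
|---|---|---|---|---|
| 180 | 178 | 15 | 0.9848 | 0.9726 |
| 255 | 252 | 24 | 0.9800 | 0.9682 |
| 330 | 326 | 33 | 0.9783 | 0.9676 |

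One late event at the limit reverses the verdict at every sample size. The missing-data rule matters too. If protocol 20.4.4.4 reduces n to 242 or 314 (95% of 255 and 330), the posterior for 24 or 33 events is 0.9652 or 0.9612: a fail with no new event. At 15/171 it is 0.9755, still a pass.

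**4. Pass at the look, fail at 12 months.** Assume 7% of subjects have a PAE by the look and a further share L has a first PAE afterwards. L is an assumption. With q = L/0.93 and n unchanged (SAP carry-forward), the probability is Σ over e≤y of P(Bin(n,0.07)=e) × P(Bin(n−e,q)>y−e):

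| L | N=180 | N=255 | N=330 |
|---|---|---|---|
| 0.1% | 1.5% | 0.7% | 0.3% |
| 0.5% | 7.9% | 4.3% | 1.9% |
| 1.0% | 16.8% | 10.6% | 5.5% |

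With no dropout (limits 16/180, 24/255, 33/330) and q = L, the 0.5% row is 6.1%, 4.3%, 2.0% and the 1.0% row is 13.3%, 10.4%, 5.6%.

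**5. Error rate for the 12-month endpoint.** Set the true 12-month rate to 14%, of which L arises after the look. The early test passes with probability P(Bin(n, 0.14−L)≤y):

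| L | N=180 | N=255 | N=330 |
|---|---|---|---|
| 0.1% | 1.8% | 2.3% | 2.6% |
| 0.5% | 2.5% | 3.5% | 4.0% |
| 1.0% | 3.9% | 5.7% | 6.8% |
| 12-month test | 1.6% | 2.1% | 2.3% |

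**6. How often each path is taken.** In Table 3.a at 65% effectiveness, early success occurs in 0.8316 of trials and overall success in 0.8395, so 0.8395 − 0.8316 = 0.79% succeed only at the end. At 60% effectiveness it is 0.6749 − 0.6202 = 5.47%.

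**The case against.** The strongest reply is that little turns on this in practice.

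- The endpoint is headed acute safety, its core window is 7 days, and SAP 7.4.1.1 discloses the exceptions. This stands as context, but disclosure does not say which test is confirmatory.
- The clash between passages changes a trial verdict only when effectiveness is won at the end: 0.79% of trials at 65% effectiveness. This stands for the clash. It does not reach the early-success path (83% of trials), where late events are never tested.
- The late rate is unknown. Protocol 6.4.1 says PV stenosis and fistula have not been reported with pulsed field energy, and its figure of under 4% is for RF and for all PV stenosis, not late cases. Wave II scans only symptomatic subjects. On the realistic schedule, 30%, 38% and 30% of the time from day 7 to month 12 is unseen at the look (N=180, 255, 330). Under a constant hazard, 0.5–1.0% after the look would imply 1.3–3.4% after day 7 (0.5/0.38 to 1.0/0.30), which is a lot beside a planned composite of 7%. This stands: the higher rows are illustrations, not forecasts.

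A reader might infer three stronger things that the documents do not support:

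- **That late events are ignored after early success.** SAP 7.4.1.2 still reports the 12-month endpoint with its sensitivity analyses, including the exact upper bound and the tipping point. Late events are left out of the test, not the report.
- **That the 2.5% error is breached.** That depends on the assumed rate. At 0.1% the early test passes with probability 1.8%, 2.3% and 2.6%.
- **That a second look inflates the safety error.** Later data can only add events or, under the protocol's rule, remove event-free subjects, so a re-test can only turn a pass into a fail.

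**Conclusion.** The conflict is real and should be resolved. The stated reason for treating the early test as final, that all outcomes are known, is contradicted by the plan's own definitions: three components have no end date and a fourth needs 12 months. Whether such events enter the 14% test depends on the passage followed and on whether effectiveness crosses 0.9975.

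That the decision is fragile at the limit (one event) follows from the stated rule and dropout. How often it would matter cannot be known from the documents: under 2% of trials at a 0.1% late rate, rising to 6–17% at 1.0%. These figures assume 7% up to the look, independent events and the SAP's carry-forward. If late events are very rare, the SAP's view that the two tests barely differ is numerically fair; the wording still has to be reconciled.

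**What to change.** 1. Keep the early-look safety test as the safety half of the early-success claim. In SAP 10.4 and protocol 20.4.4.2 and 20.4.4.3, delete the statements that all safety outcomes are known or available and that this test is the final analysis; align SAP 7.4.1.1.
2. State one PAE cut-off, 12 months, and one missing-data rule, used identically in protocol 20.4.4.2 to 20.4.4.4 and SAP 7.4.1.1, 7.4.1.2, 7.4.3 and 10.4.
3. In SAP 7.4.1.2, re-run Pr(p_S<0.14)>0.975 on 12-month data on both paths, and after early success report whether the criterion still holds.

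Cost: wording in both documents and one beta-binomial calculation, with no extra subjects or data. The downside is that an early safety claim could later be qualified by late events. Making 12-month data the only confirmatory safety test would go further: it would remove the safety half of the early-success claim, which is a design change and is not proposed here.

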10.5 Modeling for Effectiveness

For the effectiveness endpoint, the time-to-failure during the 9-month (39 weeks) post-blanking period is modeled by using a piecewise exponential model. The model has three distinct time intervals: (0, 2], (2, 8], and (8, 39] weeks. These intervals are based on a model fit to the ThermoCool Pivotal trial and the SmartTouch IDE trial. The three-piece exponential model

provides a reasonable amount of flexibility in capturing the functional form of the survival function for the effectiveness endpoint.

For the model-based approach, failure times during each interval is assumed to be exponentially distributed, with different hazard rates in each segment. The model is:

$$f(t) = \exp(-th(t)),$$

where

$$h(t) = \begin{cases} h_1 & 0 < t \leq 2; \\ h_2 & 2 < t \leq 8; \\ h_3 & 8 < t \leq 39. \end{cases}$$

A vague Gamma(1, 1) prior distribution will be used for each h in the model. Given hazard rates h_1, h_2 , and h_3 , the failure-free rate at 12 months p_E can then be estimated by $p_E = \exp(-[2h_1 + (8 - 2)h_2 + (39 - 8)h_3])$.

At the time of the early success interim analysis, the total number of primary effectiveness events and the total subject exposure time will be used to update the vague Gamma prior and obtain the posterior Gamma distribution for each segment. Then 10,000 random hazard rates will be sampled from the posterior distribution for each segment and each triplet set of hazard rates will be used to calculate p_E . The distribution of p_E is estimated based on the 10,000 calculated p_E s. If the probability of p_E being greater than 50% is greater than 0.9975(99.75%), the trial will declare early success.

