7.4.2.1 Early Success Interim Analysis of Primary Effectiveness Endpoint

At the time of the early success interim analysis, the primary effectiveness endpoint will be met if:

$$\Pr(p_E > 0.50 | x, n) > 0.9975$$

where p_E is the effectiveness success rate. If the posterior probability of the effectiveness success rate being greater than 50% is greater than 0.9975 then the study will be considered to have demonstrated effectiveness of the device at the early success interim analysis.

At the time of the early success interim analysis, the time-to-failure during the 9-month (39 weeks) post-blanking period will be modeled by using a piecewise exponential model. The model will consist of three distinct time intervals during the 9-month evaluation period: (0, 2], (2, 8], and (8, 39] weeks. Failure times during each time interval is assumed to be exponentially distributed with a different hazard rate in each segment. The model is:

$$f(t) = \exp(-th(t))$$

where

$$h(t) = \begin{cases} \lambda_1 & 0 < t \leq 2 \\ \lambda_2 & 2 < t \leq 8 \\ \lambda_3 & 8 < t \leq 39 \end{cases}$$

Vague Gamma prior distributions will be assumed for λ_1 , λ_2 , and λ_3 . Given hazard rates λ_1 , λ_2 , and λ_3 , the failure-free rate at 12 months (9 months post-blanking) p_E can then be estimated

by

$$p_E = \exp(-[2\lambda_1 + (8 - 2)\lambda_2 + (39 - 8)\lambda_3])$$

At the interim, the total number of primary effectiveness events and the total subject exposure time will be used to update the vague Gamma prior and obtain the posterior Gamma distribution for each segment. Then 10,000 random hazard rates will be sampled from the posterior distribution for each segment and each triplet set of hazard rates will be used to calculate p_E . The distribution of p_E is estimated based on the 10,000 calculated p_E s. If the probability of p_E being greater than 50% is greater than 0.9975 (99.75%), the trial will declare early success.

To investigate the robustness of the analysis result, the following sensitivity analyses will be performed in the mITT and PP analysis sets at the time of the early success interim analysis with the available data:

- **Sensitivity to Analysis Set**

The primary effectiveness endpoint will be analyzed in the mITT analysis set as a sensitivity analysis.

- **Kaplan-Meier Analysis**

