10.3.1 Prediction Probability for the Effectiveness Endpoint

To estimate the predictive probability of success for the effectiveness endpoint at each interim analysis, time-to-failure during the 9-month (39 weeks) post-blanking period will be modeled by a piecewise exponential model with 3 distinct intervals (from (0, 2], (2, 8], and (8, 39] weeks). The three-piece exponential model provides a reasonable amount of flexibility in capturing the functional form of the survival function for the effectiveness endpoint.

A vague Gamma prior distribution will be assumed for estimating each of the hazard rates:

$$h_j \sim \Gamma(\alpha=0.1, \beta=0.1) \text{ for } j = 1, 2, 3.$$

where α represents the prior number of events and β the prior exposure time. At the sample size selection interim analysis with n enrolled patients, the total number of observed events for time interval j is EV_j and the total observed exposure time for time interval j is EXP_j , assuming each patient i offers EXP_{ij} exposure for time period j . For each time interval, we update the prior distribution with the currently observed data (EV_j, EXP_j) and the resulting posterior distribution is:

$$h_j \sim \Gamma(\alpha + EV_j, \beta + EXP_j).$$

The predictive probabilities of trial success will be calculated using Monte Carlo integration. For the predictive probability of trial success at the current sample size, we assume accrual is stopped and the primary analysis is conducted after all subjects complete the 12 months follow-up. The data will be imputed in the following fashion. First, a single hazard rate, h_j , is sampled from the posterior distribution of the hazard rates for each time interval. For each patient who has not yet experienced an event, depending on which time interval their current observed time falls in, we sample an event time from an exponential distribution with mean equal to the sampled hazard rate for that time interval:

$$TTE_{ij} \sim \text{Exponential}(h_j),$$

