where TTE_{ij} represents the time to event for patient i in time period j . For patient i , his or her imputed exposure time for time interval j would be $EXP_{ij} + TTE_{ij}$. If the imputed exposure time is less than or equal to the end of the time interval, the patient will be considered an event, otherwise, the sampled h_j for the next time interval will be used to generate a time for the next time interval and impute the exposure time. The patient time will be censored at 39 weeks if the imputed time for the last time interval is greater than 39 weeks. Additionally, a censoring time will be sampled from an exponential distribution with a rate that results in the assumed attrition rate for the effectiveness endpoint at 1 year. If this censoring time is less than the event time for the subject, then the patient will be censored at this time and will not count as an event.

This process will be repeated 1000 times to generate 1000 imputed datasets. For each of these imputed datasets, success of the final analysis for the effectiveness endpoint will be assessed once assuming we would stop at the interim with the current sample size and another time assuming we use the maximum sample size of 330. The proportion of successful trials in each case provides the predictive probability of success for the effectiveness endpoint.

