10.6 Power and Type-I Error Simulations

The operating characteristics of this trial were determined through trial simulation. We hypothesized several scenarios for the underlying rates for the effectiveness and safety endpoints, and simulated the entire trial multiple times under each scenario. In each virtual trial, the interim analysis was conducted according to the pre-specified rules, and results were tracked for each trial, including whether the trial was successful on each endpoint individually and on both endpoints, whether trial success was achieved early, etc. Three different enrollment schedules were considered for the simulations corresponding to realistic, slow, and fast enrollment schedules based on logistical considerations:

Table 1. Assumed enrollment rates

	Expected number of patients per month																	
	1	2	3	4	5	6	7	8	9	10	11	12	13	14	15	16	17	18
Realistic	7.5	10.5	13.5	7.5	15	18	24	30	30	30	30	30	30	30	24			
Slow	7.2	7.2	7.2	9.6	7.2	16.8	22.8	24	24	24	24	24	24	24	24	24	24	12
Fast	10.2	10.2	5.1	10.2	11.9	15.3	17	25.5	32.3	34	34	34	34	34	23.8			

10.6 1 Effectiveness Outcome

In order to simulate the effectiveness outcome for a virtual subject, we need to simulate whether the subject has a failure and when that failure occurs. As previously discussed in section 5, a piecewise exponential time-to-failure model is assumed and calibrated to have a particular failure rate $(1 - p_E)$ at the end of follow-up. The profiles are constructed by taking advantage of the relationship:

$$p_E = \exp(-[2h_1 + (8 - 2)h_2 + (39 - 8)h_3]),$$

where p_E is the failure-free rate at 12 months. Rates from a previous study were assumed and calibrated to simulate effectiveness outcomes. From ThermoCool SSED, the reported hazard rates have the following pattern:

$$h_1 = (38.06)h_3;$$

$$h_2 = (1.71)h_3;$$

$$h_3 = (1)h_3.$$

To simulate data, we used the above multiplicative factors from ThermoCool and then found the value for h_3 , such that when multiplied by each of the assumed rates for the three time intervals, the failure-free rate at 12 months (39 weeks following 13 weeks blanking period) matches the desired scenarios. Table 2 shows the derived hazard rates that were used to simulate data for a range of assumed failure-free rates.

Table 2. Parameters to generate failure times

Failure-free Rate	Hazard Rate (h)		
	h_1	h_2	h_3
0.50	0.2248	0.0101	0.0059
0.60	0.1656	0.0074	0.0044
0.62	0.1550	0.0070	0.0041
0.65	0.1397	0.0063	0.0037

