Table 3.c Proportion of times the trial will stop at each interim for futility on 10,000 simulations for each scenario

Safety Rate	Effectiveness Rate	Overall Futility	N=180	N=255
0.07	0.60	0.0034	0.0020	0.0014
	0.62	0.0012	0.0008	0.0004
	0.65	0.0003	0.0003	0.0000

	0.70	0.0001	0.0001	0.0000
--	------	--------	--------	--------

Tables 4.a, 4.c, 5.a, and 5.c provide the estimated power and futility proportions under the slow and fast scenarios. Tables 4.b and 5.b provide the estimated type-I errors under the slow and fast scenarios.

Table 4.a Estimated power for slow enrollment assumption based on 10,000 simulations

Safety Rate	Effectiveness Rate	Overall Power	Win Effect	Win Safety	N=180	N=255	N=330	Early Success
0.07	0.60	0.6758	0.7377	0.9085	0.3768	0.2621	0.3611	0.6410
	0.62	0.7769	0.8624	0.8975	0.4711	0.3021	0.2268	0.7595
	0.65	0.8336	0.9469	0.8788	0.6111	0.2949	0.0940	0.8307
	0.70	0.8399	0.9956	0.8437	0.8121	0.1782	0.0097	0.8399

Table 4.b Estimated Type-I error for slow enrollment assumption based on 25,000 simulations

Safety Rate	Effectiveness Rate	Type-I error	95% C.I
0.14	0.99999	0.0182	[0.0166 , 0.0199]
0.00001	0.50	0.0167	[0.0151 , 0.0184]

Table 4.c Proportion of times the trial will stop at each interim for futility for slow enrollment assumption based on 10,000 simulations

Safety Rate	Effectiveness Rate	Overall Futility	N=180	N=255
0.07	0.60	0.0037	0.0023	0.0014
	0.62	0.0011	0.0009	0.0002
	0.65	0.0002	0.0002	0.0000
	0.70	0.0000	0.0000	0.0000

Table 5.a Estimated power for fast enrollment assumption based on 10,000 simulations

Safety Rate	Effectiveness Rate	Power	Win Effect	Win Safety	N=180	N=255	N=330	Early Success
0.07	0.60	0.6777	0.7284	0.9212	0.3584	0.2110	0.4306	0.5995
	0.62	0.7702	0.8439	0.9059	0.4316	0.2460	0.3224	0.7223
	0.65	0.8407	0.9459	0.8863	0.5641	0.2576	0.1783	0.8315
	0.70	0.8499	0.9953	0.8540	0.7604	0.1972	0.0424	0.8493

Table 5.b Estimated Type-I error for fast enrollment assumption based on 25,000 simulations

Safety Rate	Effectiveness Rate	Type-I error	95% C.I
0.14	0.99999	0.0172	[0.0156 , 0.0189]

0.00001	0.50	0.0159	[0.0144 , 0.0175]
---------	------	--------	-------------------

Table 5.c Proportion of times the trial will stop at each interim for futility for fast enrollment assumption based on 10,000 simulations

Safety Rate	Effectiveness Rate	Overall Futility	N=180	N=255
0.07	0.60	0.0034	0.0024	0.0010
	0.62	0.0019	0.0014	0.0005
	0.65	0.0003	0.0003	0.0000
	0.70	0.0001	0.0001	0.0000

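### The Gamma(1, 1) prior for the early-success look is not vague on the weekly scale, differs without a stated reason from the prior for sample-size selection, and the imputation text confuses mean with rate

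*SAP*

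**What the plan says.** The Wave II SAP uses one piecewise exponential model, with intervals (0, 2], (2, 8] and (8, 39] weeks after blanking, for two purposes.

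- **Sample-size selection (10.3.1).** The prior on each hazard is "h_j \sim \Gamma(\alpha=0.1, \beta=0.1"), with alpha defined as prior events and beta as prior exposure.
- **Early success (10.4 and 10.5).** 10.4 points forward: "The posterior probability is estimated based on the proposed model in the next section". 10.5 then states: "A vague Gamma(1, 1) prior distribution will be used for each h in the model". The criterion is a posterior probability above 0.9975 that p_E exceeds 50%.

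Both priors are called vague. The main text (7.4.2.1) gives no parameters and says only that the events and exposure will "update the vague Gamma prior and obtain the posterior Gamma distribution for each segment". Protocol 20.4.4.1 also says only that the Gamma priors are vague, and 20.4.4.2 refers the early look back to that model without naming a second prior.

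On imputation at the sample-size looks, 10.3.1 says "we sample an event time from an exponential distribution with mean equal to the sampled hazard rate for that time interval", and the next line writes Exponential(h_j). It adds: "If the imputed exposure time is less than or equal to the end of the time interval, the patient will be considered an event".

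**The concern.** Early success supports the CE Mark filing, so the prior behind that look is part of a decision rule. The word vague suggests to a DMC or regulator that the prior has no material influence. Whether that is true depends on the time unit and on the quantity tested, which is p_E and not the hazards. Two priors that differ tenfold in weight, under the same label, also leave unclear whether the difference is intended.

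The imputation sentence matters because an independent statistician runs these looks. An exponential variable with hazard h_j has mean 1/h_j. Code that followed the sentence literally would give wrong predictive probabilities.

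**Working it through.** **Unit and scale.** 10.5 gives p_E = exp(-[2h1 + 6h2 + 31h3]), so the interval lengths are in weeks. 10.6 calibrates h3 so that "the failure-free rate at 12 months (39 weeks following 13 weeks blanking period) matches the desired scenarios". With h1 = 38.06 h3 and h2 = 1.71 h3,

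h3 = -ln(p_E) / (2 × 38.06 + 6 × 1.71 + 31) = -ln(p_E) / 117.38.

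At p_E = 0.65 this gives 0.1397, 0.0063 and 0.0037 per week, which reproduces Table 2. The 0.50, 0.60, 0.62 and 0.70 rows also reproduce.

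**What the priors imply.** Both have mean 1 event per week, about 7, 159 and 270 times the Table 2 hazards at 65%. The prior mean of p_E is the product over intervals of (b/(b + L))^a, with L = 2, 6, 31. The other rows come from Monte Carlo draws.

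| | Gamma(1, 1) | Gamma(0.1, 0.1) |
|---|---|---|
| Prior mean p_E | 1/(3 × 7 × 32) = 0.0015 | 0.275 |
| Prior median p_E | 9e-14 | 0.004 |
| Prior Pr(p_E > 0.5) | 0.0001 | 0.28 |

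**Effect on the posterior.** The posterior is Gamma(a + events, b + exposure). Relative to Gamma(0.1, 0.1), Gamma(1, 1) adds 0.9 of an event and 0.9 of a week to each interval. Take exposures of 296, 733 and 1995 patient-weeks (an assumed case near N = 180 at a true 62%) with 46, 5 and 8 events. The added cumulative hazard is about 0.9 × (2/296 + 6/733 + 31/1995) = 0.9 × 0.0305 = 0.027. The posterior mean of p_E falls from 0.621 to 0.605. Pr(p_E > 0.5) is 0.9977 with Gamma(0.1, 0.1), a pass, and 0.9931 with Gamma(1, 1), a fail. With the later counts and the exposure fixed, the largest first-interval count that passes is 46 with Gamma(0.1, 0.1) and 41 with Gamma(1, 1).

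**Effect in the adaptive design.** These are simulations with realistic enrolment, the Table 2 hazard pattern, 15% yearly drop-out and 300 imputations per look.

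| Early effectiveness success | Gamma(0.1, 0.1) | Gamma(1, 1) | Loss |
|---|---|---|---|
| True 65%, first program | 92.0% | 85.5% | 6.5 points |
| True 65%, second program | 91.5% | 84.0% | about 7.5 points |
| True 60%, first program | 54.0% | 39.4% | 14.6 points |

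The first program ran 600 to 1,200 trials per scenario and the second 2,000. A third run gave about 0.94 against 0.85 at 65%. Two other drop-out conventions gave losses of 11 to 12 points at 65% (0.861 against 0.744; 0.895 against 0.783), and one of them gave 13.6 points at 60% (0.454 against 0.319). In the first program, under every convention, no trial passed with Gamma(1, 1) and failed with Gamma(0.1, 0.1).

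Effectiveness success at either the early look or the final test was 98.3% against 97.8% at 65% in the first program (98.1% against 97.9% in the second), and 73.1% against 70.6% at 60%.

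**Table 3.a.** Its early success figures, which include safety, were not reproduced. At 65% it gives 0.8316; the first program gives 0.853 with Gamma(0.1, 0.1) and 0.796 with Gamma(1, 1). At 60% it gives 0.6202, against 0.41 to 0.51 and 0.29 to 0.38 across conventions. The SAP does not fully state how its simulation handled drop-out, so this does not show which prior was used.

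**Mean or rate.** At the 65% hazards, rate h_j gives a chance of an event within each interval of 1 - exp(-2 × 0.1397) = 0.24, then 0.04 and 0.11. Mean h_j gives about 1.00 in each. In the first interval the mean event time would be 0.14 weeks and not 1/0.1397 = 7.2 weeks, so almost every pending subject would be imputed as a failure. Table 3.c ("Proportion of times the trial will stop at each interim for futility on 10,000 simulations for each scenario") shows overall futility of 0.0003 at 65%, which is incompatible with that coding.

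**The case against.** The strongest reply is that this is editorial. Both priors are printed with their parameters, so each look can be coded. Gamma(1, 1) carries three pseudo-events against 59 observed in the worked case, and a more cautious prior for a claim than for prediction is a legitimate choice. Gamma(0.1, 0.1) is not neutral either: its mean is also 1 event per week and its prior median p_E is 0.004. All of this stands, and it is why the point is minor. It does not justify the label vague, and it does not supply the missing reason.

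A reader might infer a larger loss. With N held at 180, early effectiveness success at 65% is 0.75 to 0.77 against 0.62 to 0.65, a loss of 12 to 14 points. That is not the design's loss: N stays at 180 only when predictive probability exceeds 90% or futility is met, and other trials go on to 255 or 330.

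A reader might also infer that the sample-size simulations used the wrong mean. Exponential(h_j) on the next line and Table 3.c both indicate that the rate was intended and coded.

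Finally, comparing within-interval exposure with an interval's end would stretch the intervals to 2, 8 and 39 weeks and turn a true 65% into about 62%. The text allows a cumulative clock, which the 39-week censoring rule suggests. This is loose notation and not a demonstrated error.

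**Conclusion.** The point holds as a minor one. Gamma(1, 1) on weekly hazards is strongly pessimistic for p_E, is mislabelled as vague, and differs from the 10.3.1 prior without explanation. It lowers estimated p_E by about 1 to 2 points. It lowers the probability of early effectiveness success by about 6.5 to 8 points at a true 65% and about 15 points at 60%. These losses are simulation estimates: they depend on the drop-out convention (up to about 12 points at 65% under others) and are not reconciled with Table 3.a.

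The documents do not support a claim of inflated type I error, because the prior makes early success harder. A missed early success only defers to the final Beta(1, 1) test, and at 65% eventual effectiveness success changes by half a point or less. Nor do the documents show that Tables 3 to 5 are wrong, since the prior behind them is not stated.

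The mean-for-rate sentence in 10.3.1 is a definite text error with serious consequences only if coded literally.

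**What to change.** - **Prior.** In SAP 7.4.2.1, 10.3.1 and 10.5, state one weakly informative prior for both uses, with beta in patient-weeks; the existing Gamma(0.1, 0.1) would serve. Alternatively, keep Gamma(1, 1) in 10.5, drop vague and state that it is deliberately conservative.
- **Imputation.** In 10.3.1, say that the rate equals the sampled hazard (mean 1/h_j), and that imputed time is cumulative from the end of blanking.
- **Simulations.** Confirm which prior produced Tables 3 to 5, and rerun them only if it differs from the final text.

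Keeping Gamma(1, 1) costs only wording. Moving to Gamma(0.1, 0.1) raises false early effectiveness success at a true 50% from about 0.001 to about 0.003 (fixed N of 180 or 330). If Table 3.b was run with Gamma(1, 1), adding a full rise of about 0.0025 to its 0.0168 gives about 0.019, still below 2.5%. An adaptive run with drop-out completely at random gave 1.50% and 1.58%. This assumes drop-outs are excluded from the final test, as SAP 7.4.3 states. Counting them as successes gave 4.4% and 4.6%, which is an effect of that rule and not of the prior.
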